This scan will be collected as participants are instructed to “rest, allow their minds to wonder and not to think of anything in particular”.

Saliva sample and affect rating #14

(L) Diffusion Tensor Imaging – DTI (Seq 3-6, 15 min)

This scan will be collected as participants are instructed to “rest, allow their minds to wonder and not to think of anything in particular”.

Participants will then be de-instrumented (chest electrodes removed) and recover their personal belongings that could not be introduced in the MRI room.

We expect all participants to perform all tasks adequately. The total scan time is (1 + 1 + 12 + 5 + 5 + 11 + 5 + 5 + 6 + 6 + 6 + 15 min) 90 minutes. The scanner will be booked for 90 minutes for each participant to accommodate saliva sample #11, instrumentation/de-instrumentation with EKG, time between tasks, and additional setup time.

Finally, participants will be debriefed on the nature of the stress reactivity tasks and the reason for deception. The debriefing script has been uploaded to this protocol (Appendix #7). Specifically, the social-evaluative component is meant to maximize neuroendocrine stress responses (67), and understanding these profiles allows insights into physiological stress functions that are predictive of many health problems. Participants will be reassured that this task was meant to elicit a physiological stress response, not to evaluate them as a person, and that they did very well. Participants will be invited to ask the study staff any question they may have.

(10) Take Home Protocol:

(A) Saliva collection: Starting a week from the study visit, participants will be instructed to provide saliva samples on three non-consecutive weekdays separated by one day. Each participant will receive an iPad with a custom made home logbook

Protocol Summary Form

application prompting them to provide four 1 mL saliva samples:

(1) upon awakening, (2) +30 minutes after awakening, (3) +45 minutes after awakening, and (4) before bedtime. Participants will then be given a Medication Event Monitoring System (MEMS 6 TrackCap Monitor, Aardex Ltd., Switzerland) cap container with the salivettes, which time stamps usage of each salivette. In addition, the application will record awakening time, sample collection times, and affect ratings. These measures will insure compliance and document any deviation from the protocol. Instructions for home collection of saliva samples are provided in the Home Logbook application and will be reviewed with the study coordinator at the end of Day 2. The Home Logbook application content is attached with the instruments for review (Appendix #10).

(B) Fecal sample collection: Along with the saliva samples, participants will be provided with a sample collection kit (collection tube, spatula and toilet hat) for fecal collection. The container will be provided into a large sealed "Ziplock" bag. Instruction for fecal collection will be watched with the study coordinator at the end of Day 2 (https://www.youtube.com/watch?v=ytr_hmJdHqM) and an instructions sheet (attached for review in Appendix #11) will be provided to all participants along with the container.

(C) Actigraph: Participant sleep and activity will be monitored over 7 days. Participants will wear a wrist actigraph, a device that detects body movement and weighs about 2 ounces. It is worn comfortably around the wrist, similar to a wristwatch, and will be left in place for the entire 7 days. A pre-stamped express courier box (FedEx) will be provided to participants to return samples upon completion.

(11) Study monitor: Although we do not anticipate any adverse effects of the study procedures, at all times during the study protocol a clinician will be on call in the event that a participant would become distressed. The identified medical doctors are [name] and [name]. The Division of Behavioral Medicine, where the laboratory stressor is conducted, has on call clinical psychologists and social workers.

To establish the within-person and technical variability in key study outcomes, we will perform "repeat" visits on two healthy volunteers. This will provide essential information on some novel mitochondrial parameters that are measured in the MiSBIE study (cell bioenergetics, cell-free mitochondrial DNA, metabolic markers), including how they may vary within a person over time, relative to between-person differences. These difficult to obtain data will allow us to quantify intra-individual variation over months-to-years, thus providing an empirical basis upon which to evaluate the magnitude of differences among the primary study outcomes between study groups.

Protocol Summary Form

For this purpose, we will obtain blood samples from two individuals at multiple points over the study period. These repeated (MiRep) visits will not be complete study visits, and are therefore not considered as MiSBIE visits for study monitoring purposes. Each visit will take no longer than 15 minutes and will be completed by a trained phlebotomist or by the study nurse. Consent will be completed prior to the blood draw, all study procedures other than the blood draw will be crossed out prior to obtaining a signature by the study coordinator.

References

7. McEwen BS. Stress, adaptation, and disease. Allostasis and allostatic load. *Ann N Y Acad Sci.* 1998;840:33-44.

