exaggerated epigenetic responses to stress. We will isolate sub-types of peripheral blood mononuclear cells at baseline to map genome-wide cytosine methylation levels. Pre- and post-stress blood samples will also be collected to track stress reactive differences by pyrosequencing of target genes linked to stress regulation and brain remodelling. Results from this aim will complement those of Aim 1 by defining stress reactivity at the sub-cellular, molecular levels.

Aim 3: Map brain-wide neural connectivity patterns in m.3243A>G and single mtDNA deletion patients, and determine if this mediate abnormal peripheral stress reactivity.

Combining measurements of peripheral stress physiology with functional neuroimaging (fMRI-BOLD), our team and others have shown that neuroendocrine, inflammatory, and cardiovascular reactivity to stress can be predicted from discrete

activation patterns among specific brain regions in healthy adults. Furthermore, the brain is an organ primarily affected in mitochondrial diseases and functional connectivity is sensitive to energetic defects, but the nature and impact of these alterations in human mitochondrial disease is unknown. *We hypothesize that patients with mitochondrial defects will exhibit abnormal patterns of resting state and task- elicited neural connectivity, including the executive network, which will statistically mediate alterations in physiological stress reactivity.* On a second visit (Day 2), we will perform structural and functional whole-brain neuroimaging of default mode network and tasks selected to match the stress reactivity on Day 1.

Taken together, this translational study will establish how neural connectivity is altered in mitochondrial disease, and begin to untangle neural pathways that may translate mitochondrial dysfunction into abnormal physiological dysregulation. This study will be the first to test the role of mitochondria in mediating mind-body processes. The resulting papers will inform future work in various fields including clinical mitochondrial medicine and neurology, psycho-neuro-endocrinology, psycho- neuro- immunology, and psychosomatic medicine.

Aim 4: To establish the within-person and technical variability in key study outcomes, two healthy volunteers will “repeat” visits to obtain blood samples up to 10 timepoints over the study period.

To establish the within-person and technical variability in key study outcomes, we will

Protocol Summary Form

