- (1) Recruitment: Patients with mitochondrial disease and healthy age/sex/race/physical activity level-matched controls will be recruited. As part of existing clinical care, some patients will have undergone (a) neuropsychological assessment, (b) metabolic assessment and (c) structural magnetic resonance imaging (MRI) as part of the diagnostic services of the Clinical Research Center for Muscular Dystrophy and Related Diseases Laboratory. From this patient pool, those molecularly identified to carry mtDNA defects (m.3243A>G, single deletion) will be provided with a study brochure and invited to sign a form agreeing to be contacted for future research. Potential participants will be contacted directly by the clinical coordinator or study coordinator who will provide information concerning the MiSBIE study and assess inclusion/exclusion criteria over the phone or in person. Should potential participants be interested in the study, they will be forwarded consent forms for their review.

We will screen participants for COVID symptoms at the following timepoints: during the initial screening call: the Monday night before the participant arrives, the Tuesday morning of study activities and the Wednesday morning of study activities. We will take the participant's temperature before starting study activities. We have a no-touch thermometer used for other MiSBIE procedures and have the required expertise to perform this measure.

Protocol Summary Form

[figure not shown]

Figure 1. Diagram illustrating study design and workflow.

Protocol Summary Form

For participants who agree to participate in the study, the a 2-day visit at the Columbia University Irving Medical Center will be scheduled and transportation/lodging arranged. Outside participants will be housed at the Edge Hotel (Washington Heights, [name]), and given detailed instructions to follow prior to their arrival.

(2) Initial Blood Draw and Biological Samples Collection: On the first outpatient visit (Day 1), a fasting blood draw to index allostatic load and cell isolation for mitochondrial function measurements and DNA/RNA analyses. Participants will first arrive at the Division of Behavioral Medicine, Presbyterian Hospital, 15th floor at 9:00am and will be greeted by [name], the MiSBIE study coordinator. Participants will have been instructed not to eat or drink beverages other than water starting at midnight the previous day.

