(5) Stress Reactivity–Recovery Paradigm: After the lunch, participants will have an IV line placed and be instrumented with physiological data acquisition equipment. Participants will be exposed to a standardized socio-evaluative laboratory challenge (58, 59). Participants will be asked to perform a simulated public speaking task, consisting of 2 min of preparation for a speech defending themselves against an alleged transgression followed by 3 min of videotaped speech delivery, as previously described (58, 59) (please find the protocol attached in Appendix #6). Throughout, we will collect repeated measures of blood (cortisol, ACTH, catecholamines, inflammatory cytokines), saliva (cortisol), and physiological monitoring (blood pressure, heart rate variability, galvanic skin response, and respiration). Research assistant [name] and [name] will monitor physiological data collection during the session and equip participants. This stress paradigm session consists of a five-part protocol:

(A) Participants will be equipped with:

Protocol Summary Form

- a. A 3-lead ECG to monitor of heart rate
- b. A finger cuff blood pressure sensor to monitor blood pressure
- c. Skin conductance surface device to monitor sympathetic nervous system activity (sweating)
- d. Two elastic breathing bands on the chest and abdomen.

(B) Participants will rest for 30 minutes in a calm room and asked to refrain from any other medium (e.g., smartphones) that could be a source of distraction. This will avoid to introduce variability in inter-individual responses. This will allow them to acclimate to their surroundings and to the equipment (e.g., ECG electrodes, finger cuff).

(C) Participants will be exposed to a socio-evaluative stress (58, 59) that induces significant psychophysiological responses among multiple systems. Psychosocial stress is induced by simulating videotaping and that these video recordings will be analyzed for speech performance by comparing their performance with those of other participants. Eight (10) mL of blood for plasma (5ml) and serum (5ml) will be collected via the venous catheter at eight defined time-points relative to the onset of the SECPT (-5, +5, +10, +20, +30, +60, +90 and +120 minutes), for a total of 80 mL of blood. Time points are illustrated in Figure 2.

[figure not shown]

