Figure 2. Expected kinetics of stress biomarkers after the socio-evaluative stress. BP = blood pressure; CORT = cortisol; E = epinephrine; HR = heart rate; IL-6 = interleukin-6; NE = norepinephrine.

Affect ratings will be collected at each time point on an iPad to measure subjective feelings of positive and negative affect (calmness and nervousness, see attached in appendix #1.3).

Protocol Summary Form

In addition, 1 mL of saliva will be collected with salivettes (Starsted) at each time point. A sterile cotton swab will be introduced in the participant's mouth, soaks with saliva for a period of approximately 2-3 minutes, and is placed back into the tube for subsequent saliva extraction by centrifugation. Oral (sub- lingual) and epidermal (anterior part of neck, back of the dominant hand) temperature will be measured non-invasively at the same time points using a no-touch infrared thermometer (AccuMed AT2102 or HTD8808) to detect thermal changes during stress reactivity and recovery.

At the last time point (+120 minutes), an additional 8.5 mL of blood will be collected to isolate PBMCs to assess effects of stress on epigenetic modifications of DNA and gene expression on sub-populations of cells and one EDTA coated tube (2ml) for complete blood count on whole blood, which totals 10.5ml.

Total blood volume drawn including the fasting morning collection and stress reactivity is approximately 190.5 mL (100 mL baseline for AL, mitochondrial function, and DNA/RNA) + (10 x 8 = 80 mL for stress reactivity biomarkers) + (10.5 mL for DNA/RNA)]. This volume does not exceed the prescribed limit for adult individuals above 110lb of body weight (200mL), and it is less than half the volume of a standard blood donation (approximately 500 mL). After the 120min time point, the venous catheter will be removed.

(D) Deep breathing: Five minutes later, participants will be asked to perform a paced deep breathing exercise with visual feedback lasting two minutes while heart rate is recorded. This will enable assessment of autonomic regulation through breathing.

(E) Standing: Sit-to-stand posture changes elicit changes in heart rate and blood pressure. Participants will be asked to go from the sitting position and stand for 5 minutes. Then sit down again.

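### Aim 2's stress-reactivity contrast has no listed cell sample just before the stressor; by elimination its baseline is the fasting morning draw, two meals earlier

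*Protocol*

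**What the plan says.** Aim 2 (Protocol, Specific Aims and Hypotheses) has a baseline part and a reactivity part. For the first: "We will isolate sub-types of peripheral blood mononuclear cells at baseline to map genome-wide cytosine methylation levels". For the second, patients are expected to show "exaggerated epigenetic responses to stress", and the data are described as follows: "Pre- and post-stress blood samples will also be collected to track stress reactive differences by pyrosequencing of target genes linked to stress regulation".

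Study Procedures list these Day 1 draws:

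- **Morning, section (2).** Participants arrive at the "15th floor at 9:00am", having fasted from midnight, for "a fasting blood draw to index allostatic load and cell isolation for mitochondrial function measurements and DNA/RNA analyses". The tube list includes five 8.5 mL acid citrate dextrose (ACD) tubes for cells and one 2 mL EDTA tube.
- **Stress session, section (5)(C), −5 to +120 minutes.** Each sample is 10 "mL of blood for plasma (5ml) and serum (5ml) will be collected via the venous catheter at eight defined time-points". No cell tube is listed at −5 minutes.
- **Post-stress cells, section (5)(C).** "At the last time point (+120 minutes), an additional 8.5 mL of blood will be collected to isolate PBMCs to assess effects of stress on" DNA modification and gene expression in cell sub-populations. A 2 mL EDTA tube for a blood count is taken with it.

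The protocol's blood-volume tally mentions DNA/RNA in two components only: the 100 mL morning draw and the 10.5 mL draw at +120 minutes. The SAP lists five outcomes. None is epigenetic, and it contains no analysis of the Aim 2 contrast.

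**The concern.** A pre-to-post change measures a response to the stressor only if little else changes between the two samples. Here a good deal does. After the morning draw come breakfast, spirometry, a medical examination, lunch, placement of an IV line and a rest period, and only then the stressor. No unstressed session is described that would show what these do on their own.

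The circulating markers do not have this problem, because plasma, serum and saliva are all sampled at −5 minutes. The cell-based outcome of Aim 2 lacks that control. What is at stake is the reading of a positive result: a larger morning-to-afternoon change in patients could be reported as exaggerated stress reactivity when it reflects a different response to eating or to time of day. The protocol's own rationale is that mitochondrial defects alter metabolic, neuroendocrine and immune regulation, so equal responses in the two groups are not a safe default.

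**Working it through.** **1. Is there room in the plan for another cell draw?** Inputs are the tube list in section (2) and the volumes in section (5)(C).

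- Morning: 1×2 + 2×5 + 5×2.7 + 2×8 + 2×8 + 5×8.5 = 2 + 10 + 13.5 + 16 + 16 + 42.5 = 100 mL.
- Stress session: 8 × (5 + 5) = 80 mL.
- Extra at +120: 8.5 + 2 = 10.5 mL.
- Total: 100 + 80 + 10.5 = 190.5 mL.

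This reproduces the protocol's 190.5 mL exactly. No blood is left unallocated for a cell sample just before the stressor.

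**2. How far apart are the two cell samples?** The documents give no clock time for the stressor, so it has to be bounded.

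- *Forward from 9:00am, stated durations only:* examination 101 + lunch 30 + rest 30 + 5 (from −5 to onset) + 120 = 286 min, so +120 falls no earlier than about 13:46. Allowing an assumed 30 to 120 min for the untimed steps gives 14:16 to 15:46.
- *Backward from the time estimation task:* make-up calls for this task are set at 3 to 5 PM to match the usual timing. Listed steps between +120 and the task: 5 + 2 + 5 + 0.5 + 1.5 + 10 + 10 = 34 min at least. The task takes about 20 min, so finishing by 17:00 means starting between 15:00 and 16:40. That puts +120 at about 14:26 to 16:06.
- *Gap, with the morning draw assumed at 9:30:* 14:26 − 9:30 = 4 h 56 min (4.9 h); 16:06 − 9:30 = 6 h 36 min (6.6 h).
- *Share of the gap before the stressor:* (4.9 − 2)/4.9 = 59%; (6.6 − 2)/6.6 = 70%. Both meals fall in that part.

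**3. What does each contrast estimate?** Let S be the effect of the stressor and C the combined effect of feeding, clock time and earlier procedures.

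- Change within controls: S_c + C_c. Change within patients: S_p + C_p.
- Difference in change: (S_p − S_c) + (C_p − C_c).

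The within-group change never isolates S. The group difference isolates S_p − S_c only if C_p = C_c. As an illustration in arbitrary units, with S = 0 in both groups, C_c = 1 and C_p = 1.5, the group difference is 0.5 with no stress effect at all. The documents give no value for C_p − C_c, so the size of any bias is unknown.

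**The case against.** Several points on the other side are sound.

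- **The hypothesis compares groups.** Controls follow the same schedule and are matched on age, sex and activity, so shared feeding and time-of-day effects cancel. A reader might infer that the design cannot separate stress from these effects under any comparison. The documents do not support that: what remains is a group-specific response to feeding or time of day, which is plausible but unquantified.
- **The protocol never calls the morning draw pre-stress.** A reader might infer that it was designated as such. It was not. Aim 2 says pre- and post-stress samples are collected in addition to the baseline cells, which could mean a separate sample; the tube list ties the morning ACD tubes to mitochondrial function, and only the introduction to section (2) and the tally link that draw to DNA/RNA. The study diagrams and data collection form are not in the text and may show more. The identification is by elimination, though the volume tally leaves no alternative.
- **Cell mix is partly handled.** Cell sub-populations are to be analysed, and EDTA tubes are drawn both in the morning and at +120. This helps with shifts in composition, not with direct fed-state or diurnal effects within a cell type.
- **The reach is narrow.** A reader might infer damage to the SAP outcomes. None is epigenetic, and the cortisol outcome is based on saliva, which is collected at −5 minutes. The SAP already reports results, so an amendment may reach few participants.

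The Aim 4 repeat visits do not fill the gap: they involve two volunteers, do not name methylation, and describe no same-day morning and afternoon pair.

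**Conclusion.** The concern holds for the reactivity half of Aim 2. As the procedures stand, the only cells available as a pre-stress baseline come from the fasting morning draw, about 4.9 to 6.6 hours and two meals before the +120 minute sample, with 2 hours of that after the stressor. A within-group change cannot be attributed to stress. A patient-control difference in change can be, on the unstated assumption that both groups respond equally to feeding and time of day.

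The order of draws and meals is stated in the protocol. The clock times are inferred, the 9:30 draw is an assumption, and the identity of the pre-stress sample is by elimination. The baseline methylation comparison is not affected.

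**What to change.** Reconcile Aim 2 with section (5)(C) by stating which cells are the pre-stress sample. If cells were kept at −5 minutes outside the described procedures, say so.

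For future participants:

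- Move one of the five morning 8.5 mL ACD tubes to the −5 minute draw, through the catheter already in place.
- Keep the morning EDTA tube, because the allostatic load outcome in the SAP uses fasting hematological measures, and add a second 2 mL EDTA tube at −5 minutes. The total becomes 190.5 − 8.5 + 8.5 + 2 = 192.5 mL, under the protocol's stated 200 mL limit. Adding both tubes without moving one would give 190.5 + 8.5 + 2 = 201 mL, above it.
- Define the Aim 2 stress response as +120 minus −5 minutes, within cell type.

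The cost is an amendment, one more cell isolation per participant, and 8.5/42.5 = 20% less morning blood for cells. Check that the remaining 34 mL still supports the mitochondrial assays, including the lymphocyte respiration outcome in the SAP.

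This shortens the contrast to 125 minutes, with both samples after lunch. It reduces the confounding but does not remove it: the time since lunch still differs between samples, and there is still no unstressed session.

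For participants already studied, report the contrast as a morning-fasting to afternoon-post-stress change, do not attribute it to stress, and state the equal-response assumption beside any group difference. This needs no new samples.

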Mitochondrial Stress, Brain Imaging, and Epigenetics (MiSBIE)

Statistical Analysis Plan

NCT04831424

October 6, 2023

Outcome Measures

Primary Outcome Measure:

1. *Average TSST-induced elevation in cortisol*

This is designed to measure cortisol reactivity to the trier social stress test (TSST), quantified from salivary cortisol (LC-MS) over an 8-timepoints timecourse. The elevation will be measured as the area under the curve (AUC) for the cortisol time course.

[Time Frame: Day 1 post challenge (approximately 2 hours)]

SAP and Results: The AUC analysis for salivary cortisol reactivity to the TSST utilized two metrics: AUCg, where the ground is set at zero, and AUCi, where the ground is set at the baseline level. Given the non-Gaussian distribution of both groups, we applied the Mann-Whitney U test to compare the Control and MitoD groups. For AUCg, the MitoD group's cortisol level was 31.9% higher than the Control (64.49 ng/mL vs. 48.97 ng/mL), but this difference was not statistically significant ($p = 0.40$). The AUCi showed a significant 86.8% higher level in the MitoD group compared to the Control (20.91 ng/mL vs. 11.21 ng/mL, $p = 0.049$).

2. *Average allostatic load index*

Groups will be compared on a quantitative allostatic load (AL) index integrating baseline fasting measures of neuroendocrine, immune and metabolic systems, urinary catecholamines, hematological measures, and hair/diurnal cortisol levels.

[Time Frame: Blood collected on Day 1]

SAP and Results: We calculated allostatic load using the standard count-based index (Juster et al., 2024). In short, for each biomarker, we calculated the 12.5th, 25th, 75th, and 87.5th percentile according to sex-specific reference ranges. We used these percentiles to score each variable as either dysregulated (1) or not dysregulated (0) and summed each variable's score to produce the final allostatic load value. Using the non-parametric Mann-Whitney test, we find that allostatic load is significantly higher in participants with mitochondrial disease than in controls ($p = 0.018$), with a medium effect size (Hedge's $g = 0.52$).

Secondary Outcome Measures:

3. *Average TSST-induced elevation in heart rate*

Groups will be compared on heart rate (HR) as a measure of cardiovascular reactivity to stress, monitored using a continuous 3-lead ECG. The elevation will be computed from the baseline HR to the peak HR reached during the TSST.

[Time Frame: Day 1 post challenge (approximately 2 hours)]

SAP and Results: Given the non-Gaussian distribution of this data, we conducted the Kruskal-Wallis test to examine differences in heart rate elevation among four clinical groups.

Given the non-Gaussian distribution of this data, we conducted a Mann-Whitney U test to examine differences in heart rate elevation between the control group and combined mitochondrial disease groups (m.3243A>G, MELAS, and deletion). The Mann-Whitney U test indicated that there were no statistically significant differences in heart rate elevation among the groups ($p = 0.42$, $d = 0.27$).

4. ***Correlation between anxiety and mitochondrial respiration***

The association between mitochondrial respiration using extracellular flux analysis (Seahorse) on blood lymphocytes, and anxiety symptoms measured using the state and trait anxiety inventory (STAI), will be quantified by a linear regression across all study participants.

[Time Frame: Day 1]

SAP and Results: Mitochondrial respiration in isolated lymphocytes was measured on a XFe96 Seahorse extracellular flux analyzer. In brief, 0.25M live lymphocytes were seeded in an extracellular flux cell culture plate, and a MitoStressTest was performed following the manufacturer's protocol. Baseline oxygen consumption rate (OCR) was corrected for non-mitochondrial respiration (OCR after rotenone/antimycinA injection) to quantify basal mitochondrial respiration. Linear regression analysis across all participants revealed that higher values of mitochondrial respiration in isolated lymphocytes are associated with lower *state* anxiety ($R^2 = 0.05$, $p = 0.04$). However, the relationship between mitochondrial respiration and *trait* anxiety was not significant ($R^2 = 0.01$, $p = 0.49$).

5. ***Average neuropsychological function***

Groups will be compared on the fluency/initiation domain of executive functioning assessed using the Delis-Kaplan Executive Function System (D-KEFS) test.

[Time Frame: Day 2 neuropsychological session]

SAP and Results: To calculate a standardized score (z-score), we first adjusted raw neuropsychological scores for age using data from the reference group (control group). Predicted values from this model, representing age-adjusted scores, were used to calculate z-scores (Andrade, 2021). Next, we conducted a Mann-Whitney U test to examine differences in z-scores for D-KEFS letter fluency, a measure of fluency and initiation, between two groups: the control group and combined mitochondrial disease groups (m.3243A>G, MELAS, and deletion). The Mann-Whitney U test results indicated that there were no statistically significant differences in the fluency/initiation domain among the groups ($d = 0.11$, $p = 0.61$).

References:

Andrade, C. (2021). Z Scores, Standard Scores, and Composite Test Scores Explained. *Indian J Psychol Med*, 43(6), 555-557. <https://doi.org/10.1177/02537176211046525>

Juster, R.-P., Cipriani, E., Kerr, P., & DuBois, L. Z. (2024). Configurations, comparisons, and challenges calculating allostatic load. *Psychoneuroendocrinology*, 160, 106787. <https://doi.org/https://doi.org/10.1016/j.psyneuen.2023.106787>

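### The SAP's rules for the two primary outcomes appear only beside their results, and no earlier rule is shown for the cortisol AUC form, the allostatic-load scoring or the pooled two-group test

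*SAP*

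**What the plan says.** Each outcome in the SAP has two parts: a short entry, mostly in the future tense, and a past-tense paragraph that combines method and result.

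**Primary Outcome 1 (cortisol).** The forward-looking entry says "The elevation will be measured as the area under the curve (AUC) for the cortisol time course". It names neither AUCg nor AUCi, and no test. The results paragraph begins "SAP and Results: The AUC analysis for salivary cortisol reactivity to the TSST utilized two metrics" and continues "Given the non-Gaussian distribution of both groups, we applied the Mann-Whitney U test to compare the Control and MitoD groups". AUCg is reported as "but this difference was not statistically significant ($p = 0.40", and AUCi as "20.91 ng/mL vs. 11.21 ng/mL, $p = 0.049" and significant. Neither metric is ranked above the other.

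**Primary Outcome 2 (allostatic load).** The forward-looking entry lists the systems and sample types that feed the index. It gives no biomarker list, cut-off, tail or test. The results paragraph computes four percentiles per biomarker within sex (12.5th, 25th, 75th, 87.5th), scores each biomarker 0 or 1, and reports a Mann-Whitney p = 0.018 with Hedges' g = 0.52. It does not say which percentile and which tail apply to which biomarker. The scoring source is listed as "2024). Configurations, comparisons, and challenges calculating allostatic load", while the SAP carries the date "October 6, 2023".

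**Secondary Outcome 3 (heart rate).** The paragraph says "Given the non-Gaussian distribution of this data, we conducted the Kruskal-Wallis test" for four clinical groups, gives no result for that test, and then reports a Mann-Whitney test with the disease groups pooled.

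The protocol (Specific Aims and Hypotheses, Aim 1) states a directional hypothesis for allostatic load and stress reactivity. It has no statistical section, no alpha and no multiplicity rule.

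**The concern.** A statistical analysis plan lets a reader treat a p-value as a test of a rule set beforehand. Here the only text that states the primary rules was written with the results in hand, and the entries that look forward leave the decisive choices open.

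The cortisol conclusion rests on one of those choices. One AUC was planned, two were analysed, and they fall on opposite sides of 0.05. For allostatic load, the plan leaves open how the score is built. For both outcomes, pooling three disease samples into one group is likewise not stated in advance.

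At stake is the status of the two primary claims, not whether the analyses are sensible.

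**Working it through.** **1. Inputs.** From the SAP: AUCg p = 0.40, with group values 64.49 and 48.97 ng/mL; AUCi p = 0.049, with 20.91 and 11.21 ng/mL; allostatic load p = 0.018. A two-sided family-wise alpha of 0.05 is an assumption, because neither document states one.

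**2. Reproducing the SAP's own figures.** The p-values come from rank tests on individual data. No analysed n or spread is given, so they cannot be recomputed. The percentage differences can be checked:
- AUCg: 64.49/48.97 − 1 = 31.7% (SAP: 31.9%).
- AUCi: 20.91/11.21 − 1 = 86.5% (SAP: 86.8%).

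Rounding of the printed values does not close these gaps (ranges 31.67% to 31.72% and 86.40% to 86.66%). They are small and do not affect this point.

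**3. What is fixed in advance and what is not.**

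| Choice | Forward-looking entry | Results text |
|---|---|---|
| Cortisol summary | an AUC, form not stated | AUCg and AUCi, unranked |
| Cortisol test | none | Mann-Whitney, because the data looked non-Gaussian |
| Allostatic-load biomarkers, cut-offs, tails | systems and sample types only | four percentiles, no assignment to biomarkers |
| Allostatic-load test | none | Mann-Whitney, no reason given |
| Pooling of disease groups | not stated | one disease group against controls |
| Multiplicity | none | none |

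The test is explicitly tied to the observed distribution for Outcomes 1 and 3 only.

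**4. How far the claims depend on the unfixed choice.** Holm's method orders the m p-values from smallest to largest, multiplies them by m, m − 1, …, 1, and lets no adjusted value fall below the one before it.

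- *All three reported primary tests (m = 3):* allostatic load 3 × 0.018 = 0.054; AUCi 2 × 0.049 = 0.098; AUCg 1 × 0.40 = 0.40. None is below 0.05.
- *AUCi as the only cortisol metric (m = 2):* allostatic load 2 × 0.018 = 0.036; AUCi 1 × 0.049 = 0.049. Both are below 0.05.
- *AUCg as the only cortisol metric (m = 2):* allostatic load 0.036; AUCg 0.40. Only allostatic load is below 0.05.

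Bonferroni gives 0.054, 0.147 and 1.00 for the three tests. With AUCi alone it gives 0.036 and 0.098.

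The number of primary claims that survive is therefore none, one or two, depending on a metric and a correction that the documents do not fix.

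**The case against.** The case for the sponsor is substantial, and most of it stands.

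- **The reporting is open.** Both AUC forms are shown, including the null one, and the reason for the rank test is stated. The SAP does not use the word confirmatory. This is true. What is missing is a ranking of the two metrics and a label for their status.
- **Choosing a rank test for skewed data costs almost nothing.** In a null simulation, a Shapiro test was followed by Welch's t or Mann-Whitney. It assumed 45/45 and 60/30 participants, normal and lognormal data, and 8,000 runs each. The error rate was 4.6% to 5.3%. The SAP also uses Mann-Whitney for every two-group comparison, including the null ones. The choice of test is thus the weakest part of the point; the AUC form and the scoring rule carry it.
- **The allostatic-load index is called standard.** It may have been settled well before the analysis. That is possible, but a general method does not fix the biomarkers, cut-offs and tails.

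A reader might infer more than the documents support:

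- *That the SAP date is false, or that the scoring was set after October 2023.* The source is cited as 2024, but its DOI contains 2023, so earlier availability cannot be excluded. A late citation also does not date the rule.
- *That the allostatic-load test was picked from the data.* The SAP gives no distribution-based reason for that outcome.
- *That a specific inflated error rate applies.* This would need the correlation between the competing analyses and the order of decisions. Neither is given.
- *That all five outcomes are post hoc.* Outcome 4 announces its linear regression across all participants in the future tense, and Outcome 3 fixes baseline to peak.

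**Conclusion.** The point holds as a gap in what is shown. Neither document contains a rule, stated apart from the results, for the AUC form, the allostatic-load biomarkers, cut-offs and tails, or the pooled two-group test. The p-values of 0.049 and 0.018 therefore cannot be read as tests of pre-specified rules on this evidence.

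The size is best seen in the adjusted values. Over the three reported primary tests the smallest Holm value is 0.054, whereas with AUCi as the sole cortisol metric both claims stay below 0.05, one of them only just (0.049). This rests on the assumed two-sided family-wise alpha of 0.05 and on treating the three reported tests as one family.

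The documents do not show that either p-value is wrong, or that any rule was chosen because of its result. An earlier dated plan that states these rules would answer the point; none is in the documents supplied.

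**What to change.** If an earlier dated rule exists, cite it in the SAP for each of the AUC form, the allostatic-load biomarkers, cut-offs and tails, and the pooled comparison. If not:

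1. Label the AUCg, AUCi and allostatic-load analyses as not pre-specified (exploratory).
2. Report AUCg and AUCi with equal weight.
3. Remove the significance wording from AUCi p = 0.049 and allostatic load p = 0.018, or show multiplicity-adjusted p-values and name the family of tests.
4. Give effect estimates with 95% CIs and the number analysed per group.
5. State which percentile and tail apply to each biomarker, so that the score can be reproduced.
6. Reconcile the SAP date with the source cited as 2024, for example by a version history.

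Outcomes 1 to 5 need not be relabelled as a block. A separate confirmatory subset is not proposed: the documents do not say that enrolment is still open, and with one participant seen per week such a subset could be very small.

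The cost is SAP wording and a few interval estimates from data already in hand. The downside is that the stated primary claims become weaker.
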